4.2 Statistical Analysis

All analyses will be performed for all subjects combined and by treatment group. Only summary statistics will be used.

All continuous variables (eg, birth weight, body temperature, PCO₂) will be summarized using number (n), mean, standard deviation (SD), median, 1st quartile, 3rd quartile, minimum, and maximum. All discrete variables (eg, sex, AEs, common complications of prematurity), will be summarized using frequency (n) and percent.

The treatment difference (delta) between active and control treatments will be calculated for the primary and secondary efficacy endpoints. The delta calculated may be used to plan additional studies and as supporting evidence of efficacy.

4.2.1 Primary Efficacy Endpoint

The primary endpoint is the occurrence of respiratory failure due to RDS, defined as the number of subjects who need intubation for surfactant administration and/or intubation (including intratracheal catheter placement) for MV or all-cause death within 28 days of life.

4.2.2 Key Secondary Endpoints

Key secondary endpoints include the occurrence of respiratory failure due to RDS or death within 72 hours; the occurrence of respiratory failure due to RDS (without death) within 72 hours and 28 days of life; and time to respiratory failure due to RDS or death within 72 hours of life and 28 days of life, presented by treatment group.

BPD is defined as the need for supplemental oxygen above room air (21%) at 36 weeks PMA. The number and percent of subjects who develop BPD by 36 weeks PMA will be summarized by treatment group. The number and percent of subjects who are alive and without BPD at 36 weeks PMA will be summarized by treatment group. Furthermore, the severity of BPD, based on NIH

definition, will be assessed. The severity of BPD is defined as, in addition to supplemental oxygen $> 21\%$ for at least 28 days, breathing room air (21%) or 22% at 36 weeks PMA or discharge is mild, moderate is $> 22\%$ to $< 30\%$ oxygen at 36 weeks PMA or discharge, and severe is $\geq 30\%$ oxygen and/or positive pressure at 36 weeks PMA or discharge. The BPD severity will be summarized by treatment group.

4.2.3 Other Secondary Endpoints

For other secondary endpoints include common complications of prematurity, gas exchange parameters (ie, FiO_2 , transcutaneous PCO_2 , SpO_2), duration of MV and oxygen requirement (the sum of all time periods using MV and supplemental oxygen through 36 weeks PMA, respectively), and duration and number of re-hospitalization and urgent care visits (through 12 months corrected age) will be summarized by treatment group. The reason for re-hospitalization and urgent care visits and respiratory medications (through 12 months corrected age) will be listed.

Common complications of prematurity through 36 weeks PMA (apnea, air leak, IVH, PVL, pulmonary hemorrhage, NEC, PDA, acquired sepsis, and ROP) will be summarized by treatment group using frequency and percent by treatment group.

Change in FiO_2 is defined as the change from baseline (initiation of treatment for active subjects or completion of patient interface setup for control subjects) through 72 hours post-randomization, and over the first 7 days of life. Change in transcutaneous PCO_2 is defined as the change from baseline (initiation of treatment for active subjects or completion of patient interface setup for control subjects) through 72 hours post-randomization. Change in transcutaneous SpO_2 is defined as the change from baseline (initiation of treatment for active subjects or completion of patient interface setup for control subjects) through 72 hours post-randomization.

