For incidence of BPD or incidence of survival survived without BPD, no subjects in the active groups and 6 subjects in the nCPAP only group developed BPD during the study. An exploratory comparison between the active and control groups was significant at p -value = 0.022 from Fisher's Exact Test. The incidence of survival without BPD was 22 (92%) and 18 (75%) subjects for the active and nCPAP only groups, respectively.

Exploratory assessment of clinical efficacy parameters, while small and potentially confounded by treatment interruptions, suggests that there was no qualitative evidence on rate of intubation; however, there was some evidence of effect in time to intubation, BPD, and fraction of inspired oxygen (FiO₂) requirements. The magnitude of the effect has not been determined and the study was not powered for comparisons between treatment groups.

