4.3.3 Other Secondary Endpoints

Other secondary endpoints of this study include the evaluation of the following:

1. Common complications of prematurity through 36 weeks PMA (IVH, periventricular leukomalacia [PVL], pulmonary hemorrhage, apnea, NEC, patent ductus arteriosus [PDA], acquired sepsis, ROP).
2. Duration of MV and oxygen requirement through 36 weeks PMA
3. Changes in FiO₂, PCO₂, and SpO₂ over the first 72 hours of life, and over the first 7 days of life for FiO₂
4. Number/duration of and reason for re-hospitalization and urgent care visits through 12 months corrected age.
5. Respiratory medications through 12 months corrected age.

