4.1 Efficacy Populations

For efficacy analyses, subjects will be summarized according to their assigned (randomized) treatment. The subjects enrolled open-label with active treatment (the first 2 subjects from each site) will not be summarized separately.

The analysis of both the primary and secondary objectives will be based on all enrolled preterm neonates (ITT population).

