4.3 Missing Data

Missing values represent a potential source of bias in a clinical trial. Hence, every effort will be undertaken to fulfill all the requirements of the protocol concerning the collection and management of data; however, some missing data is inevitable. No imputation, including last observation carried forward, will be done for the any parameters; only available data will be considered.

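### Duration of MV and of supplemental oxygen has no rule for death before 36 weeks PMA, so a death shortens the recorded duration; for BPD alone only the denominator is unstated

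*SAP*

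**What the plan says.** **Durations.** Protocol 4.3.3 lists "Duration of MV and oxygen requirement through 36 weeks PMA" among the other secondary endpoints. SAP 4.2.3 makes this operational as "the sum of all time periods using MV and supplemental oxygen through 36 weeks PMA, respectively". The SAP Executive Summary ends primary-phase follow-up at 36 weeks PMA, discharge, transfer or death. Protocol 13 leaves missing-data handling to the SAP, and SAP 4.3 says: "No imputation, including last observation carried forward, will be done for the any parameters; only available data will be considered". Neither document says what value an infant who dies contributes.

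**Use.** Duration of MV is named in the objectives (Protocol 4.1, SAP Executive Summary, SAP 1.2). SAP 4.2 calculates the treatment difference (delta) for the primary and secondary endpoints and lets it serve as support for efficacy. The SAP Executive Summary, SAP 2.2.3 and Protocol 13.2 confine delta to the primary and key secondary endpoints, which would leave out both durations.

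**BPD.** SAP 4.2.2 states: "BPD is defined as the need for supplemental oxygen above room air (21%) at 36 weeks PMA". It then plans two summaries: "The number and percent of subjects who develop BPD by 36 weeks PMA will be summarized by treatment group" and "The number and percent of subjects who are alive and without BPD at 36 weeks PMA will be summarized by treatment group". On who is counted, SAP 4.1 says: "The analysis of both the primary and secondary objectives will be based on all enrolled preterm neonates (ITT population".

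**Deaths.** All-cause death is part of the primary endpoint (SAP 4.2.1). SAP 6.3.6 summarizes mortality by arm and lists each death with its date and time.

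**The concern.** A sum of support time is easy to interpret only if every infant is observed to the same end. An infant who dies while ventilated stops adding days, so its recorded duration is lower than it would have been had it lived on support. If the partial sum enters the arm mean, the death pulls the mean down. If the infant is instead dropped under the available-data rule, the death vanishes from the summary. On neither reading does it count against the arm.

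For BPD the plan pairs the simple proportion with a measure in which death is a failure. Neither duration has such a partner. This matters because shorter support is a result the sponsor already uses: Protocol 3.2.3.5 presents numerically shorter support among infants who failed nCPAP in 03-CL-1202 as a possible clinical benefit. A duration difference from this trial could be read in the same way, or carried into the planning of the next study.

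**Working it through.** **1. Reproduce the documents' own figure.** The trial has no power calculation. The one stated figure that bears on the point is the BPD comparison in 03-CL-1401 (Protocol 2.3.2.2): 0/24 active against 6/24 control. Fisher's exact test, two-sided, gives p = 0.0219, matching the stated 0.022.

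**2. Longest possible support time.** Eligible gestational age is 26 0/7 to 32 6/7 weeks. Days from birth to 36 0/7 weeks:
- born 26 0/7: 10 weeks × 7 = 70 days
- born 32 6/7: 3 weeks + 1 day = 22 days

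**3. Effect of one death on an arm mean.** Assume continuous support until death on day 10, and compare with the same infant surviving on support to 36 weeks. Shift = (days to 36 weeks − 10) / n.

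| Born | Days lost | n = 6 (assumed) | n = 65 (planned) |
|---|---|---|---|
| 26 0/7 | 70 − 10 = 60 | 60/6 = 10.0 days | 60/65 = 0.92 days |
| 32 6/7 | 22 − 10 = 12 | 12/6 = 2.0 days | 12/65 = 0.18 days |

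These are upper bounds, because the comparison infant is taken to need support throughout. Twelve infants were enrolled (SAP Executive Summary). The documents give no split by arm, so 6 per arm is an assumption; the shift scales as 1/n.

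**4. Direction.** The shift goes to whichever arm has the death. The prior studies split both ways: 03-CL-1401 had 2 active and 0 control deaths (Protocol 2.3.2.2; control deaths = 24 − 18 alive without BPD − 6 with BPD = 0). 03-CL-1202 had 1 active and 2 control deaths (Protocol 3.2.4.2).

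**5. Does BPD have the same problem?** Protocol 2.3.2.2 reports: "The incidence of survival without BPD was 22 (92%) and 18 (75%) subjects for the active and nCPAP only groups, respectively". Its complement is BPD or death.
- 03-CL-1401: BPD alone 0/24 against 6/24, difference −25.0 points. BPD or death 2/24 (8.3%) against 6/24 (25.0%), difference −16.7 points, Fisher p = 0.245.
- 03-CL-1401 among survivors only: 0/22 against 6/24, Fisher p = 0.022.
- Both studies pooled (Protocol Table 2-1): BPD alone 14/166 (8.4%) against 16/95 (16.8%), difference −8.4 points. Adding deaths, (14 + 3)/166 = 10.2% against (16 + 2)/95 = 18.9%, difference −8.7 points. This assumes that no infant had both events and that the 03-CL-1202 deaths fell before 36 weeks.

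So BPD alone and BPD or death can differ in one small study and barely differ in the pooled data. SAP 4.2.2 plans the measure that reveals the difference.

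**The case against.** The strongest reply is that little turns on this. The study stopped at 12 infants, SAP 8.3 rules out testing, and SAP 6.4.3 and 6.3.6 list support data and deaths by subject, so a duration cut short by death could be spotted. Most sections that mention delta exclude the other secondary endpoints. The 10.0-day figure is an extreme case: Protocol 3.1 expects only 10-15% of infants in the 26 to 28 week stratum. All of this stands, and it limits the size of the point. It does not supply a rule for death, and SAP 4.2 still lets a secondary-endpoint delta count as support for efficacy.

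Two stronger readings are tempting, and the documents do not support either.

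- **That a death generally looks like a benefit on duration.** In 03-CL-1202 the nCPAP failure rate was 44%, so 56% did not fail. An infant ventilated for 10 days before dying records more MV than one never ventilated. The value is low only relative to that infant's own course had it survived on support.
- **That the SAP scores a dead infant as free of BPD.** No section says so. SAP 4.1 (all enrolled) would keep the infant in the denominator; SAP 4.3 (available data only) would remove it. Table 2-1 of the Protocol keeps all 24 active infants of 03-CL-1401 despite two deaths, but that describes a prior study and is not a rule for this one. Survival without BPD is a key secondary endpoint here, and delta is planned for it.

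**Conclusion.** The gap is real for the two durations: a plain sum, follow-up that ends at death, and no partner measure that counts death. One death could lower an arm mean by at most 2.0 to 10.0 days with 6 infants per arm, or 0.18 to 0.92 days at the planned 65. These figures assume death on day 10, continuous support, a comparison infant supported to 36 weeks and, for the first range, an even split of the 12. There is no distortion without deaths, and nothing in the plan fixes its direction. It affects descriptive differences only.

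For BPD the protection is largely in place. What remains is an unstated denominator, on which SAP 4.1 and 4.3 conflict, and the fact that SAP section 11 names no table for BPD, survival without BPD, mortality or either duration. A reader might infer from 03-CL-1401 that BPD alone will mislead in favour of active treatment. The pooled difference, −8.4 against −8.7 points, does not bear that out.

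**What to change.** - **SAP 4.2.3:** add days alive and free of MV, and days alive and free of supplemental oxygen, to 28 days of life, with death by then scored as zero. Day 28 gives every infant the same maximum. A 36-week horizon would run from 22 to 70 days by gestational age, and the score would then largely reflect gestational age.
- **Raw duration:** keep it to 36 weeks, shown by vital status with the number of deaths. This also covers deaths after day 28, which the new measure does not penalize.
- **Discharge or transfer before the horizon:** state the rule, since either truncates the sum in the same way.
- **Delta:** reconcile SAP 4.2 with the Executive Summary and SAP 2.2.3 on whether it covers other secondary endpoints.
- **SAP 4.2.2 and section 11:** state the BPD-alone denominator, and show BPD, deaths and survival without BPD in one named table.

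The cost is a few lines of SAP text and two derived variables. Times of support changes (Protocol 8.7.5) and of death (Protocol 4.4) are already collected, and the oxygen measure uses the same intervals as the planned oxygen sum. The downside is that a combined scale is a little harder to read than plain duration, and scoring death as zero is a convention that should be stated as such.

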4.3 Missing Data

Missing values represent a potential source of bias in a clinical trial. Hence, every effort will be undertaken to fulfill all the requirements of the protocol concerning the collection and management of data; however, some missing data is inevitable. No imputation, including last observation carried forward, will be done for the any parameters; only available data will be considered.

4.4 Subgroup Analyses

Presentations by subgroup (sex, race, ethnic origin, country/region) or by gestational age strata will not be performed due to the small number of subjects enrolled.

5 TECHNICAL PERFORMANCE OF THE DEVICE

The technical performance of the device will be summarized for each active treatment. The incidence of the following will be summarized: total treatment duration, total amount dispensed, number of pauses, total time paused, ventilator/CPAP tubing detachments, aerosol tube detachments, aerosol tube condensate obstruction, proximal pressure port obstructions, (the number of the detachments that are intentional and uninterntional will also be recorded), study drug leakage (either liquid or aerosol) before the subject interface, occurrence of any alarm signals (before, during, and after dosing), automatic system shutdowns, , inability to maintain nCPAP (with a description), occurrence of any error codes, ADS temperature alerts (high or low). In addition, the weight and/or volume of liquid in all traps will be summarized as continuous variables. Statistical comparisons between active treatment groups are not planned.

Incomplete treatments with reasons and/or explanations will be listed.

6 SAFETY ANALYSES

6.1 Safety Population

The safety population is defined as all subjects who received any study medication, active or sham. Subjects will be included in the treatment group for the treatment actually received (if different than the group that they were randomized). The subjects enrolled open-label with active treatment (the first 2 subjects from each site) will be pooled with data from double-blind portion of the study. All safety assessments will be based on this population.

Safety analyses will be summarized by all subjects combined and by country or region.

6.2 Extent of Exposure

All subjects randomized to active treatment are to receive at least one dose of study medication. Subjects will receive two consecutive 50 minutes of aerosolized lucinactant in the first dose. The number of subjects who receive a repeat dose (50 minutes), the number of doses received, the amount of treatment received (based on time of treatment), and the number of subjects whose study treatment is terminated early will be summarized.

6.3 Adverse Events

All treatment-emergent AEs (TEAEs; AEs occurring at or after randomization) will be coded by preferred term and system organ class (SOC) from the Medical Dictionary for Regulatory

Activities (MedDRA), version 16.1 or above, and will be reviewed by the medical monitor or designee. All TEAEs will be summarized as categorical variables (frequency and percent) by treatment group unless otherwise indicated. TEAEs that are related to the device (ADEs) will be summarized with all AEs and separately. TEAEs will not be compared between treatment groups.

6.3.1 Peri-Dosing AEs

The incidence of peri-dosing events (ie, bradycardia, desaturation, gagging/regurgitation, apnea, and pallor) will be summarized.

In addition, the incidence of complications related to the placement of bi-nasal prongs (bleeding, apparent obstruction to the nares, occlusion of the prongs, nasal irritation, and other) will be summarized by treatment group.

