1.2 Schedule of Activities (SOA)

Measurement/Procedure	Primary Phase Through 36 Weeks PMA				Post-36 Weeks Visit	Follow-Up Period (≤ 12 Months Corr. Age)
	Screening	Primary Period (Days 1-3)	Extended Period (Days 4-7)	Final Period (Day 8 to Final Visit ¹)		
Informed Consent	X					
Inclusion/Exclusion Criteria	X					
Demographics	X					
Maternal/Birth/Medical Hx	X					
Chest Radiograph ²	X	X	X			
Respiratory support	X	X	X	X		X
Physical Examination	X			X		
Randomization		X				
Study Treatment Admin.		X				
Technical Perform. of Device		X				
PCO ₂		X ^{3,4}				
FiO ₂ , SpO ₂ , Vital Signs, PEEP		X ^{3,4}	X ⁵			
Respiratory ventilation/support				X	X	X
AEs and ADEs		X	X	X		
Concomitant Medication		X	X	X	X ⁶	X ⁶
Complications of Prematurity				X		
Final Visit/Discharge				X	X ⁷	
Hosp. and Emerg. Visits Info.					X	X
Health Assessment						X
Abbrev. PE, Neuro. Exam						X ⁸
Growth Assessment						X ⁸

Note: Day 1 for all subjects is the day of the initial study treatment.

¹ 36 weeks PMA, hospital transfer, or hospital discharge (whichever occurs first). Subjects must remain in the study until 28 days of life, unless transferred/discharged or death.

² A chest radiograph must be obtained prior to dosing to confirm RDS diagnosis and absence of air leak. An additional chest radiograph is required prior to any intubation if such a procedure does not delay or compromise the emergent care of the subject.

³ Documented at randomization, every 30 minutes after randomization until initiation of study treatment.

⁴ Study Days 1-3: time 0 (study treatment initiation), 10, 20, 30, 40, 50, 60, 70, 80, 90, 100, 110, 120, 130, 140, 150 minutes (± 3 minutes) after initiation (through 70 minutes for repeat treatments); 3 ± 0.5, 6 ± 1, 9 ± 1, 12 ± 1, 18 ± 2, 24 ± 2, 36 ± 2, 48 ± 2, 60 ± 2 and 72 ± 2 hours after initiation.

⁵ Recorded at 08:00 and 20:00 daily through Day 7.

⁶ Bronchodilators, steroids, and palivizumab (Synagis) use only.

⁷ If discharge occurs after 36 weeks PMA.

⁸ 12-months corrected age only.

TABLE OF CONTENTS

TITLE PAGE	1
1 LUCINACTANT FOR INHALATION PROTOCOL 03-CL-1702	3
1.1 Summary	3
1.2 Schedule of Activities (SOA)	16
TABLE OF CONTENTS	17
LIST OF ABBREVIATIONS	22
2 INTRODUCTION	24
2.1 Treatment of Neonatal Respiratory Distress Syndrome	25
2.1.1 Continuous Positive Airway Pressure in Neonatal Respiratory Distress Syndrome	25
2.1.2 Unmet Medical Need for Aerosolized Surfactant Replacement Therapy	26

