6.4.1 Aerosol Delivery in the Active Treatment Groups

Randomization must occur within 6 hours of birth. Study treatment with lucinactant for inhalation must be initiated as soon as possible (within 2 hours of randomization), but no later than 8 hours after birth. For the first 2 subjects at each site and subjects randomized to the active study treatment group, the duration of the initial treatment is 100 minutes (corresponding to 160 mg TPL/kg). The subject will be connected to the study nCPAP and study airway connector (see Section [8.7.3](#)). Following this change in the airway circuit, subjects will need to stabilize for at least 15 minutes before being connected to the ADS.

Subjects are eligible to receive up to 3 repeat treatments (a total of 4 treatments) of the treatment to which they are originally assigned; however, repeat doses for the active treatment will be 80 mg TPL/kg. Repeat treatments will be given as soon as 20 minutes from completion of the previous treatments up to 36 hours after completion of randomization if the subjects meet repeat treatment criteria (Section [6.6](#)). However, all subjects are to receive a repeat treatment, unless the subject is on an FiO₂ of 0.21 (room air) at the end of study treatment dosing (ie, 50 minutes after initiation). Repeat treatments will not be given if it is unsafe to do so in the judgment of the PI.

Preparations for a repeat treatment should begin at the end of the study treatment (eg, reconstituted drug product requested from pharmacy). If a subject is above room air at 100 minutes (or 50 minutes for repeat dosing) after initiation but subsequently is at room air at the time the repeat treatment is ready to be delivered, the dosing team may elect to not deliver the repeat dose. If study drug was reconstituted but not used, it may be used (treatment initiated) up to 5 hours after reconstitution if the subject requalifies within this time. Note that the reconstituted product may only be given to the subject to which it was assigned; it cannot be used for another subject.

The PI will follow routine practice guidelines to determine when a subject in either treatment group requires rescue surfactant therapy or escalation of respiratory support. All study treatments are masked (see Section 6.6).

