6.6 Repeat Treatments

Up to 3 repeat treatments will be administered to each subject, regardless of treatment group assignment, up to 36 hours following randomization. For each subject, repeat treatments will occur if repeat treatment criteria are met, unless it is unsafe to do so in the judgment of the investigator. It is required that all subjects receive a repeat treatment after the previous treatment, unless the subject is on an FiO₂ of 0.21 (room air). Masking procedures used for the initial treatment will be followed for repeat treatments (see Section 6.7).

The repeat treatment criteria are defined as follows:

- Time: \geq 20 minutes from completion of the previous treatment (up to 36 hours following randomization)
- Respiratory support: Subject has a need for $\text{FiO}_2 > 0.21$ to maintain SpO_2 of 90% to 95%.

The repeat treatment should occur as soon as possible after the 20-minute time period has elapsed, but no more than 1 hour after meeting criteria.

As with the initial treatment, the randomization/inventory system will be used to receive the drug kit assignments, and all other procedures that were performed for the initial treatment will be followed for the administration of the repeat treatments.

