9 ADVERSE EVENT REPORTING

Information regarding the occurrence of AEs will be assessed from the time of randomization until completion of 36 weeks PMA/Final Visit. Incidence of ADEs will be assessed from the time of randomization until completion of Study Day 7.

For purposes of this study, the following will be considered AEs of special interest:

1. AEs during the dosing period (ie, peri-dosing events), defined as the following AEs with an onset time \leq 2 hours from the time of initiating study treatment:
 - Apnea (lack of inspiratory air movement sustained for \geq 20 seconds and coincident with at least one of the following: $\text{SpO}_2 < 80\%$, $\text{HR} < 100 \text{ bpm}$, requirement for PPV administered manually or mechanically through any patient interface)
 - Bradycardia (heart rate $< 100 \text{ bpm}$ sustained for ≥ 20 seconds)
 - Desaturation ($\text{SpO}_2 < 80\%$ sustained for ≥ 20 seconds)
 - Gagging/regurgitation
 - Pallor
2. Complications related to placement of the patient interface as identified by the following:
 - Bleeding
 - Apparent obstruction of the nares
 - Occlusion of the interface requiring removal and replacement
 - Nasal irritation (erythema of nares or septum, inflammation of nares or septum)
3. Air leak is considered an AE of special interest if it occurs at any time during the study. Examples of air leak include the following:
 - Pneumothorax
 - PIE
 - Pneumomediastinum
 - Pneumopericardium
 - Subcutaneous emphysema

Complications of prematurity, including IVH, PVL, pulmonary hemorrhage, apnea, NEC, PDA, acquired sepsis, and ROP, will be summarized but are not considered AEs of special interest.

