17 APPENDICES

Appendix 1 - Protocol Definitions

Definitions	
Air leak, pulmonary	Chest radiographic evidence of air leak (pneumothorax, PIE, pneumomediastinum, pneumopericardium, subcutaneous emphysema). An air leak is considered an AE of special interest if it occurs at any time during the study.
Apnea	A lack of inspiratory air movement sustained for ≥ 20 seconds and coincident with at least one of the following: (a) $\text{SpO}_2 < 80\%$ (not necessarily ≥ 20 seconds), (b) $\text{HR} < 100 \text{ bpm}$ (not necessarily ≥ 20 seconds), or (c) requirement for positive pressure ventilation administered manually or mechanically through any patient interface.
Bradycardia	A heart rate $< 100 \text{ bpm}$ sustained for ≥ 20 seconds
Bronchopulmonary dysplasia (BPD)	The need for oxygen supplementation ($\text{FiO}_2 > 0.21$), regardless of source, at 36 weeks PMA.
Desaturation	$\text{SpO}_2 < 80\%$, sustained for ≥ 20 seconds
Final Visit	The final study visit is to occur at 36 weeks PMA (or 28 days of life, whichever occurs last), at the time of hospital discharge, or at the time of hospital transfer (whichever occurs first). If the neonate dies, the final visit will be considered the last study data reported before death.
Gestational age	Gestational age of the subject based on the mother's last menstrual period (post-menstrual age [PMA]) based on best obstetrical estimate or ultrasound.
Non-invasive ventilation (NIV)	Any respiratory support device which generates a constant or variable (eg, bi-level) positive pressure regardless of whether synchronized to the subject's inspirations and uses a patient interface on the subject's face.
Study treatment	Receipt of active or sham treatment, either initially or as a repeat. Masking procedures for the initial treatment will be followed for repeat treatments.
Oxygen-only support	Delivery of oxygen without the generation of pressure above ambient pressure (eg, standard-flow nasal cannula). Although all forms of respiratory support may provide $\text{FiO}_2 > 0.21$, for this study oxygen-only support refers to modes that deliver oxygen without pressure.

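### A per-infant peri-dosing incidence mixes event risk per treatment with the number of 2-hour windows, which is set after randomization; show the initial treatment separately

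*SAP*

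**What the plan says.** Protocol Section 9 makes this group the first of the adverse events of special interest: "AEs during the dosing period (ie, peri-dosing events), defined as the following AEs with an onset time" of no more than "2 hours from the time of initiating study treatment". Appendix 1 defines study treatment as "Receipt of active or sham treatment, either initially or as a repeat".

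Repeats are not optional extras. Protocol 6.4.1 states: "Subjects are eligible to receive up to 3 repeat treatments (a total of 4 treatments) of the treatment to which they are originally assigned". Protocol 6.6 adds: "It is required that all subjects receive a repeat treatment after the previous treatment", "unless the subject is on an FiO₂ of 0.21 (room air"), subject to investigator judgement on safety and a limit of 36 hours after randomization. Protocol 8.6.1 closes the other route: an infant given commercial surfactant stays in follow-up but has no further study treatment.

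On the analysis side, SAP 6.3.1 says "The incidence of peri-dosing events (ie, bradycardia, desaturation, gagging/regurgitation, apnea, and pallor) will be summarized". The general rule in SAP 6.3 is frequency and percent by arm, which points to a count of infants. Table 6.1 uses the safety population. The number of doses is summarized in SAP 3.3.2 and 6.2, but is not used as a denominator. SAP 6.3.2 tabulates apnea, bradycardia and desaturation occurring after the peri-dosing period.

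**The concern.** The number of windows an infant contributes is itself a result of treatment. An infant who reaches room air needs no repeat, one who stays above room air is given up to three, and one who is intubated or rescued has no more. If infants are counted once over all their windows, two arms with the same risk at every treatment can show different percentages because they had different numbers of treatments.

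Scheduled readings add to this: Protocol 8.1.1 and 8.1.2 repeat the 10-minute schedule for 70 minutes after each repeat starts, so detection is denser in infants with more treatments.

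At stake is the reading of acute tolerability of the aerosol. A difference, or the lack of one, could reflect the number of treatments rather than what happens at a treatment. Events that fall outside the windows move to the SAP 6.3.2 table, which shifts in the opposite direction. Gagging/regurgitation and pallor have no such companion table and would appear only among the general adverse events.

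**Working it through.** The plan states no figure on this point, so there is none to reproduce.

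**1. Window time per infant.** Inputs: 120-minute window (Protocol 9); initial treatment 100 minutes active or 110 minutes sham, repeats 50 minutes, minimum gap 20 minutes (Protocol 6.4.1, 6.4.2, 6.6). Earliest starts are 0, 120, 190 and 260 minutes (active) or 0, 130, 200 and 270 minutes (sham). The union of the windows is the same for both.

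| Repeats | Union at earliest repeats (min) | Without overlap (min) |
|---|---|---|
| 0 | 120 | 120 |
| 1 | 240 | 240 |
| 2 | 310 | 360 |
| 3 | 380 | 480 |

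The range is 380/120 = 3.2-fold to 480/120 = 4-fold.

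**2. Effect on a per-infant percentage.** Assume the same risk p in every window and both arms. With k windows, incidence = 1 − (1 − p)^k. Take p = 18%, the active-arm figure from Study 03-CL-1201 (7 of 40, Protocol 2.3.2.1), and vary it because its transfer to sham and to repeats is an assumption.

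| p | 1 window | 2 | 3 | 4 |
|---|---|---|---|---|
| 5% | 5.0% | 9.8% | 14.3% | 18.5% |
| 18% | 18.0% | 32.8% | 44.9% | 54.8% |
| 30% | 30.0% | 51.0% | 65.7% | 76.0% |

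If risk follows minutes instead, with repeats as early as allowed, the 18% row becomes 18.0%, 32.8%, 40.1% and 46.7%, from 1 − 0.82^(minutes/120).

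**3. A realistic imbalance.** Study 03-CL-1202 (Protocol 2.3.2.3) allowed two repeats. At 80 mg TPL/kg, 54% were repeated and the mean was 1.8 treatments, so P(2 repeats) = 1.8 − 1 − 0.54 = 0.26. The shares with 1, 2 and 3 windows are 0.46, 0.28 and 0.26. In the control arm 63% were repeated but no mean is given. Assume P(2 repeats) = 0.36, the value implied for the 40 mg arm (2.0 − 1 − 0.64); the control shares are then 0.37, 0.27 and 0.36.

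- Active: 0.46 × 0.180 + 0.28 × 0.328 + 0.26 × 0.449 = 29.1%
- Control: 0.37 × 0.180 + 0.27 × 0.328 + 0.36 × 0.449 = 31.7%
- Artefact: 2.5 points from unrounded values, with identical risk at every treatment

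Over p = 5% to 30% and control P(2 repeats) = 0.26 to 0.45, it runs from 0.4 to 4.7 points.

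**4. The opposite direction.** Suppose a share f of the control infants who would have had repeats is intubated or rescued first, in that arm only. Control incidence at p = 18% falls by f × [0.27 × (0.328 − 0.180) + 0.36 × (0.449 − 0.180)] = f × 13.7 points.

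| f | Control mean windows | Control incidence |
|---|---|---|
| 0% | 1.99 | 31.7% |
| 10% | 1.89 | 30.3% |
| 20% | 1.79 | 28.9% |
| 30% | 1.69 | 27.6% |

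The active figure is 29.1%, so the sign changes at f of about 2.5/13.7, or 19%. This scenario is hypothetical; it shows only that the direction is not fixed.

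**5. With the initial window alone.** Every treated infant has exactly one, so equal risk gives equal percentages (18% v 18%) whatever the repeats. That window closes at 120 minutes, no later than the earliest repeat, unless the initial treatment is cut short.

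**The case against.** The best argument against is that the reopening window is an inference. SAP 6.3.1 states neither window nor unit, and footnote 4 of the Schedule of Activities labels the first treatment "time 0 (study treatment initiation") and handles repeats separately. If only the first treatment counts, every infant has the same 2 hours and the problem disappears. That reading is possible, but Appendix 1 is the formal definition and includes repeats, and Protocol 8.1.1 also speaks of treatment initiation for repeats. An initial-only window would leave events during up to three repeat treatments out of the peri-dosing table. Either way, the SAP should say which applies.

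A reader might infer more than the documents support:

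- *That the arm improving faster must look safer.* Deterioration to intubation or rescue also removes windows (Protocol 8.6.1). In Study 03-CL-1202 active infants had more peri-dosing events than controls (Protocol 3.2.4.2), although the 80 mg arm had fewer repeats.
- *That infants with fewer repeats are watched for less time.* Adverse events are collected in everyone from randomization to 36 weeks PMA or the Final Visit. Only peri-dosing window time and the density of scheduled readings differ.
- *That the artefact is large.* Repeat distributions that give a 10- to 13-point gap can be constructed, but the documents contain none.

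The point about practical weight stands. Only 12 infants were enrolled, SAP 6.3 rules out comparing adverse events between arms, and doses by arm are shown elsewhere. If the 12 include at least two open-label active infants, at most about five are controls, and one infant is worth about 1/5 = 20 points. It is also fair that a per-infant percentage is a legitimate summary of the whole regimen, and that rates over repeat treatments compare infants selected after randomization.

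**Conclusion.** The point holds as a low-priority descriptive improvement. On the protocol's own definitions, a per-infant peri-dosing incidence combines risk per treatment with a number of windows that depends on FiO2 and on intubation or rescue after randomization. The net distortion can go either way.

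The likely size is about 2.5 points, or 0.4 to 4.7 over the range tried. That rests on four assumptions: repeat behaviour like Study 03-CL-1202, which allowed two repeats rather than three; a control split that the documents do not give; one constant risk per window in both arms; and 18% as its central value, taken from active infants in another study. Overlapping windows would make it smaller, and a third repeat could make it larger.

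With 12 infants this cannot change a formal conclusion, because none is planned. It does affect how the table can be read, and descriptive tables are all the safety output this trial will have.

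**What to change.** In SAP 6.3.1 and Table 6.1:

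1. State that the 2-hour window applies to each treatment, initial or repeat, active or sham.
2. Keep the percentage of infants with at least one peri-dosing event, labelled as covering all treatments received.
3. Beside it, by arm, give the number and percentage of infants with at least one event in the initial-treatment window. This is the like-for-like descriptive figure.
4. For repeats, give sessions with at least one event over sessions given, with a note that infants with repeats are selected on FiO2 after randomization. At the shortest spacing, consecutive repeat windows overlap by 120 − 70 = 50 minutes, so assign each event to the most recently started treatment.

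No test, per-hour rate or per-day rate is needed. Adverse event onset times (Protocol 9.1) and treatment timing and duration (Protocol 6.10) are already captured. The cost is a few lines of SAP text and one re-tabulation. The downside is a slightly larger table with small cells.
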